10.9.1	NIH Definition of Protocol Deviation	41
10.10	Publication and Data Sharing Policy.....	41
10.10.1	Human Data Sharing Plan	41
10.10.2	Genomic Data Sharing Plan.....	41
10.11	Collaborative Agreements.....	41
10.12	Conflict of Interest Policy	42
11	ABBREVIATIONS	42
12	REFERENCES	44

Abbreviated Title: COXes in MS

Version Date: 04/20/23

STATEMENT OF COMPLIANCE

The trial will be carried out in accordance with International Conference on Harmonization Good Clinical Practice (ICH GCP) and the following:

- United States (US) Code of Federal Regulations (CFR) applicable to clinical studies (45 CFR Part 46, 21 CFR Part 50, 21 CFR Part 56, 21 CFR Part 312, and/or 21 CFR Part 812)

National Institutes of Health (NIH)-funded investigators and clinical trial site staff who are responsible for the conduct, management, or oversight of NIH-funded clinical trials have completed Human Subjects Protection and ICH GCP Training.

The protocol, informed consent form(s), recruitment materials, and all participant materials will be submitted to the Institutional Review Board (IRB) for review and approval. Approval of both the protocol and the consent form must be obtained before any participant is enrolled. Any amendment to the protocol will require review and approval by the IRB before the changes are implemented to the study. In addition, all changes to the consent form will be IRB-approved; an IRB determination will be made regarding whether a new consent needs to be obtained from participants who provided consent, using a previously approved consent form.

1 PROTOCOL SUMMARY

1.1 SYNOPSIS

Title:	PET Imaging of Cyclooxygenases in Multiple Sclerosis
Study Description:	This study will examine whether cyclooxygenase 1 (COX-1) and cyclooxygenase 2 (COX-2) are elevated in the brain of individuals with Multiple Sclerosis (MS)
Objectives:	To determine whether COX-1 and COX-2 are detectable in the brains of individuals with MS.
Endpoints:	Primary endpoint: Calculation of COX-1 and COX-2 densities from [¹¹ C]PS13 and [¹¹ C]MC1 PET scans, respectively, using baseline scans and scans after blockade with ketoprofen and celecoxib, respectively. Secondary endpoint: 1) Comparison of [¹¹ C]PS13 and [¹¹ C]MC1 specific uptake in different types of MS lesions (active, chronic active, inactive) and in normal white matter. 2) Comparison of [¹¹ C]PS13 and [¹¹ C]MC1 specific uptake in the brain lesions of the same subjects
Study Population:	Sixteen (16) participants with MS will be recruited. Participants may be male or female, 18 years or older and enrolled in the HP-00079860 protocol at the University of Maryland in Baltimore (UMB).
Phase:	2
Description of Sites/Facilities	
Enrolling Participants:	This is a multisite protocol that will enroll patients from University of Maryland and screening and PET imaging will be performed at the NIH Clinical Center.
Description of Study Intervention:	Participants will be intravenously injected with up to 20 mCi of [¹¹ C]PS13 and [¹¹ C]MC1 twice, once at baseline and once after blockade by ketoprofen and celecoxib, respectively.
Study Duration:	36 months.
Participant Duration:	2-5 days.

1.2 SCHEMA

Abbreviated Title: COXes in MS

Version Date: 04/20/23

Visit 1
Time Point

Obtain informed consent. General medical history
and examination, and laboratory testing)

Visit 2-3
Time Point

Day hospital visits:
1 IV, pre-lab EKG
PET scan #1 at baseline with one tracer
PET scan #2 after blockade
Post-labs
Follow-up phone call

Visit 3-5
Time Point

Day hospital visits:
1 IV, pre-lab EKG
PET scan #1 at baseline with the other tracer
PET scan #2 after blockade
Post-labs
Follow-up phone call

1.3 SCHEDULE OF ACTIVITIES (SOA)

This study will require one to five visits, including the initial evaluation (1 day) and four PET scans (1-4 days); two PET scans for each radioligand. The screening evaluations during the initial visit will take 4-6 hours and will typically be performed in one day. Those who agree to join the study on an outpatient basis will adhere to the following schedule: during the first visit, the participant will give informed consent and complete the screening, which includes a history and physical exam. The screening evaluation will include screening labs and EKG and will typically be done on the same day. The two PET scans with each radioligand will typically occur on the same day, but they may be done on separate days.

These patients enrolled will have already been recruited under protocol HP-00079860 (In vivo assessment of meningeal inflammation and its clinical impact in multiple sclerosis by 7 Tesla MRI) at the University of Maryland, Baltimore (UMB; PI: [name]). Participants will have already undergone the study activities involved in UMB protocol HP-00079860, which includes a 7T MRI of the brain. The 7T MRI acquired under the UMB protocol will later be used for co-registration of PET, so MRI does not need to be repeated under this protocol.

Table 1

	1 st Visit / Screen	2 nd Visit	3 rd Visit	4 th Visit	5 th Visit
Informed consent	X				
History and physical exam	X				
Screening lab tests*	X				
EKG	X	On each visit with PET scan			
Brain PET scans		Up to two at each visit, no more than four total			
Safety tests for PET scans**		On each visit with PET scan			

If a blocker is given, the following set of PET scans with the other blocker must not be done earlier than two days after. The PET scans should be completed within a timeframe of two months.

*The screening lab tests are described in Section 5.2.

** Safety tests for each PET scan are described in Section 8.3.

2 INTRODUCTION

2.1 STUDY RATIONALE

Our laboratory developed two novel radioligands, [¹¹C]PS13 and [¹¹C]MC1 for PET imaging of cyclooxygenase-1 (COX-1) and cyclooxygenase-2 (COX-2), respectively. COX-1 and COX-2 are two isoforms of COX enzyme which play a key rate limiting step in the conversion of arachidonic acid (AA) into pro-inflammatory lipid metabolites called prostaglandins (PGs). COX-1 is constitutively expressed in most brain tissues whereas COX-2 is induced by inflammatory stimuli. We recently found that COX-2 was elevated and measurable in the currently symptomatic joints of patients with rheumatoid arthritis [1]. We now seek to determine whether COX-2 is measurable in the brains of participants with MS, in particular in the MS plaques.

Although MS provides the technical advantage of local areas of active inflammation, it also entails the technical disadvantage of a breakdown of the blood-brain barrier surrounding active plaques. Thus, the uptake could reflect both parent radioligand binding to COX-1 and COX-2 as well as inactive, polar radiometabolites that can spill into the compromised tissue. To address this problem, a COX-1 and COX-2 blocking agent, ketoprofen and celecoxib, will be given. Radioligand specific uptake will be blocked by ketoprofen and celecoxib, whereas the activity due to radiometabolites won't be affected.

In this way, the outcome measure will be a comparison of brain lesions at baseline and after blockade, normalized to a reference region such as the contralateral mirror image of the lesion, and thus does not require absolute quantitation with arterial plasma samples. Of course, this ratio would not determine whether COX-1 or COX-2 are globally increased in MS brain, in addition to any local increases associated with active plaques. However, arterial blood sampling seems excessively burdensome for an exploratory study. Expressed in other terms, if COX-1 or COX-2 do not detect any specific binding in MS lesions, then it's unlikely to detect a global increase compared to healthy subjects.

A reference region will be selected based on the PET scan blocked by celecoxib or ketoprofen. A true reference region has no specific/blockable binding, and a pseudo-reference region has a small amount of specific binding. The cerebellum might not be the most appropriate choice because the cerebellum is affected by diffuse inflammation in MS. This is however a problem common to all regions, since MS affects the whole brain. A more accurate reference region might be the mirror image of the ROI in the opposite hemisphere because, even if affected by generalized inflammation, the contralateral ROI would more accurately reflect the amount of nonspecific binding of the target region. A comparison with the contralateral region would track the change in COX-1 and COX-2 binding after blockade with sufficient accuracy, without the need of an arterial input function.

The MS lesions will be identified anatomically by a 7T MRI, acquired under a specific protocol of UMB (PI: [name]). The 7T MRI images include the following brain sequences: MP2RAGE (magnetization prepared 2 rapid acquisition gradient echo), MPRAGE (magnetization prepared rapid acquisition gradient echo), FLAIR (fluid attenuated inversion recovery), and a ME-GRE (multi-echo gradient recalled echo). All are 3D acquisitions and acquired both pre- and post-gadolinium contrast. All 7T MRI images will be co-registered to the pre-contrast MP2RAGE T1-weighted image at 0.5 mm³ resolution. MRI images will undergo both manual processing for MS lesion identification and classification, along with use of

automated and semi-automated tools for brain structure/tissue segmentation. PET images will also be co-registered to the pre-contrast T1-weighted MP2RAGE image, allowing interrogation of PET signal in various lesion types and brain structures. Every effort will be made to have PET study visits occur as close to the date of the 7T MRI as possible. In order to account for logistical problems, PET will be performed within 180 days before or after MRI. Similarly, the baseline/blocked scans will be performed within two months of each other. An interval of at least two days will be respected between the administration of the two blockers (ketoprofen and celecoxib). Lesions will be identified on MRI independently of the PET scans and by investigators blinded to the PET scans.

As a secondary endpoint, we will explore whether different types of MS lesions display different amounts of COX-1 and COX-2 binding. In particular, active lesions will be identified as those that show contrast enhancement with administration of gadolinium. Chronic-active lesions will be identified as those who have a paramagnetic outer rim identified on ME-GRE images that have been processed for quantitative susceptibility maps (QSM). Inactive lesions will be white matter lesions that do not meet criteria for active or chronic-active. Normal appearing white matter will be all white matter minus lesioned white matter, as determined by automated segmentation. We hypothesize that COX-1 and COX-2 binding positively correlates with the activity of the lesion.

Finally, we will determine whether the expressions of COX-1 and COX-2 are correlated by analyzing the uptake of the two tracers within the lesions of the same subjects.

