Figure 5. Human PET images of COX-2 in an individual with rheumatoid arthritis and a healthy control. Increased [¹¹C]MC1 uptake in the bilateral hand joints reflected increased COX-2 binding in a participant with rheumatoid arthritis compared to the healthy volunteer. The increased [¹¹C]MC1 uptake in the individual with rheumatoid arthritis was partially blocked by celecoxib (400 mg) but may be completely blocked by higher doses [1].

We scanned six new healthy participants under protocol 19-M-0079 (Evaluation of novel PET radioligands as inflammatory biomarkers in rheumatoid arthritis and myositis). The brain scans were fully quantitative and had an arterial input function, acquired at baseline and after blockade by 600 mg of celecoxib, a preferential COX-2 inhibitor. All subjects showed a small amount (10-20%) of displaceable COX-2 signal in the brain, measured as total distribution volume corrected for plasma free fraction of the parent radioligand. This measure of enzyme density (V_T/fp) was $95 \pm 9.5 \text{ mL/cm}^3$ at baseline and $76 \pm 4.7 \text{ mL/cm}^3$ after blockade (Fig 6).

[figure not shown]

Figure 6: VT/fp at baseline and after blockade with 600mg celecoxib in 6 healthy subjects. A small displaceable binding (10-20%) is seen in each subject.

These quantitative brain studies demonstrate that our COX-2 radioligand, [¹¹C]MC1, has the sensitivity necessary to measure the low densities of COX-2 present in healthy human brain. These studies in healthy participants complement our prior finding that [¹¹C]MC1 can detect elevated COX-2 in symptomatic, but not asymptomatic, joints in participants with rheumatoid arthritis (Shrestha et al. 2020).

Given that the same target, COX-2, is expressed in MS lesions, we expect that [¹¹C]MC1 will be able to detect an increase of COX-2 concentrations also in this population of subjects.

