3 OBJECTIVES AND ENDPOINTS

Objectives	Endpoints	Justification for Endpoints
Primary		
To determine whether COX-1 and COX-2 are detectable in the brains of participants with MS.	PET scans with [¹¹ C]PS13 and [¹¹ C]MC1 with and without blockade by ketoprofen and celecoxib.	We previously demonstrated that these radioligands are selective for COX-1 and COX-2.
Secondary		
To determine whether COX-1 and COX-2 differ in various types of MS lesions (active, chronic active, inactive) compared to normal white matter.	PET scans with [¹¹ C]PS13 and [¹¹ C]MC1 with and without blockade by ketoprofen and celecoxib.	We previously demonstrated that these radioligands are selective for COX-1 and COX-2.
To determine whether the expressions of COX-1 and COX-2 are correlated in the lesions of the same subjects	PET scans with [¹¹ C]PS13 and [¹¹ C]MC1 with and without blockade by ketoprofen and celecoxib.	We previously demonstrated that these radioligands are selective for COX-1 and COX-2.

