9 STATISTICAL CONSIDERATIONS

9.1 STATISTICAL HYPOTHESIS

- Primary Endpoint: We hypothesize that administration of ketoprofen or celecoxib will reduce COX-1 or COX-2 levels (measured as SUVR between a lesion and a reference region such as the contralateral mirror image of the lesion) in MS lesions. Please note that detectable or specific binding is defined as that which can be displaced by a COX selective inhibitor. Thus, the primary objective “detectable binding” will be assessed with the primary endpoint “displaceable binding.”
- Secondary Endpoint: 1) We hypothesize that more active MS lesions will have higher levels of COX-1 and COX-2 specific binding than less active ones, and that MS lesions will have higher binding than normal white matter. Active lesions will be identified as those that show contrast enhancement with administration of gadolinium. Chronic-active lesions will be identified as those who have a paramagnetic outer rim identified on ME-GRE images that have been processed for quantitative susceptibility maps (QSM). Inactive lesions will be white matter

lesions that do not meet criteria for active or chronic-active. Normal appearing white matter will be all white matter minus lesioned white matter. 2) We hypothesize that the expressions of COX-1 and COX-2 are correlated within the same individuals.

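### The primary SUVR has no fixed denominator, and against the favoured contralateral mirror it tests lesion excess rather than detectable COX

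*Combined protocol and SAP*

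**What the plan says.** **Denominator.** Section 2.1 describes the outcome as lesions compared at baseline and after blockade, "normalized to a reference region such as the contralateral mirror image of the lesion". Sections 9.1, 9.4.2 and 9.4.3 repeat that form, so the mirror is an example and not a fixed choice.

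**How it is chosen.** Section 2.1 states: "A reference region will be selected based on the PET scan blocked by celecoxib or ketoprofen". It separates a true reference (no blockable binding) from a pseudo-reference (a little), doubts the cerebellum, and says "A more accurate reference region might be the mirror image of the ROI in the opposite hemisphere". No threshold, timing or reader is given. On blinding it says "Lesions will be identified on MRI independently of the PET scans and by investigators blinded to the PET scans"; nothing similar covers the reference region.

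**What is to be shown.** The primary objective in Section 3 is "To determine whether COX-1 and COX-2 are detectable in the brains of participants with MS". Section 9.1 adds that "detectable or specific binding is defined as that which can be displaced by a COX selective inhibitor". Section 9.4.1 plans a two-tailed paired t-test of baseline against blocked scans.

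**What normal brain shows.** In six healthy participants given celecoxib, Section 2.2 reports: "All subjects showed a small amount (10-20%) of displaceable COX-2 signal in the brain". It also reports COX-1 throughout the brain.

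**What a null would mean.** Section 2.1 accepts that the ratio cannot show a global increase. It then argues that "if COX-1 or COX-2 do not detect any specific binding in MS lesions", a global increase over healthy subjects is unlikely to be found.

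**The concern.** The blocked scan is one half of the primary contrast, so choosing the denominator from it makes the outcome measure depend on outcome data.

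The larger problem is that the candidate regions answer different questions. A region without blockable binding lets the ratio show any displaceable binding in the lesion, which is how Section 9.1 defines detection. The mirror lets it show only what the lesion has beyond the mirror. Section 2.1 pulls both ways: its ideal is a region with no blockable binding, yet the region it prefers is brain tissue that, on the protocol's own COX-2 data, probably has some.

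At stake is the meaning of a null. Sections 3 and 9.1 would have it read as COX not detected, and Section 2.1 would extend it to no likely global increase. With the mirror, neither reading follows.

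**Working it through.** **The plan's own figures.** Section 2.2 gives mean V_T/fp of 95 at baseline and 76 after celecoxib: 1 - 76/95 = 20.0%, the top of its stated 10-20%. Section 9.2 gives 20/2 + 1 = 11 completers. No effect size or SD enters that number, so it does not depend on the denominator.

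**Model (COX-2 only).** Assumptions: V_T/fp in healthy brain stands in for SUV, and blockade is complete. Normal tissue has baseline uptake 1 and displaced fraction D = 0.10 or 0.20. The lesion has k times normal COX-2, and the reference falls by a fraction r.

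- Lesion at baseline: L0 = 1 + (k - 1)D
- Lesion after blockade: L1 = L0 - kD = 1 - D
- Fall in SUVR = 1 - L1 / [L0(1 - r)]
- Normal mirror: r = D, so the fall is 1 - 1/L0

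For example, with k = 1 and r = 0.05: 1 - 0.90/0.95 = 5.3% and 1 - 0.80/0.95 = 15.8%.

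| Lesion COX-2 | No blockable binding (r = 0) | Pseudo-reference (r = 0.05, assumed) | Normal mirror (r = D) |
|---|---|---|---|
| normal (k = 1) | 10.0 / 20.0% | 5.3 / 15.8% | 0 / 0% |
| twofold | 18.2 / 33.3% | 13.9 / 29.8% | 9.1 / 16.7% |
| threefold | 25.0 / 42.9% | 21.1 / 39.8% | 16.7 / 28.6% |

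(Entries are for D = 0.10 / 0.20.)

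**What follows from the algebra.**

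- The zero at k = 1 does not depend on noise. It also holds if blockade is only 50% or 80% complete, because both sides lose the same share.
- If COX-2 is raised equally in lesion and mirror, the ratio is 1 before and after blockade. The fall is 0% however large the increase.
- If the lesion has half the mirror's specific binding, it goes from 76 + 9.5 = 85.5 to 76 while the mirror goes from 95 to 76. SUVR rises from 0.90 to 1.00 although the lesion holds displaceable COX-2.
- Lesion tissue inside the mirror dilutes the change. With k = 2, D = 0.20 and lesion share f, the fall is 1 - (1 + 0.20f)/1.20: 16.7% at f = 0, 12.5% at f = 0.25, 8.3% at f = 0.50.

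**Effect on the verdict.** Two-sided 5% paired t-test on log SUVR change, n = 11. The documents give no SD for this change, so SDs of 5-15% are assumed. Disagreement means that one denominator gives a significant fall and the other does not. It was simulated in 40,000 trials with shared lesion noise, independent reference noise and a per-region SD equal to the SUVR SD divided by √2.

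| Lesion COX-2 | Comparison | Disagreement |
|---|---|---|
| normal | r = 0 against mirror, SD 5-15% | 54-98% |
| normal | r = 0.05 against mirror, SD 10% | 35-97% |
| twofold | r = 0 against mirror, SD 5-15% | 0-50% |
| threefold | r = 0 against mirror, SD 5-15% | 0-5% |
| fivefold or more | r = 0 against mirror, SD 5-15% | about 0% |

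For the normal lesion at SD 10%, a significant fall occurs in 88% (D = 0.10) to nearly 100% (D = 0.20) of trials against r = 0, and in 2.5% against the mirror.

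**Effect of choosing on the blocked scan.** Take two candidate regions displaced as much as the lesion (10-20%), and choose once the one whose mean change is nearest zero. Significant falls occur in about 4.4% of trials and rises in about 0.6%, instead of 2.5% each. The total stays near 5%.

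**The case against.** The protocol does not expect lesions with merely normal COX-2. Section 2.2 describes extensive COX-2 expression in MS lesions and, after monkey work, upregulation that can reach 10- to 20-fold. At such levels either denominator gives the same answer. A binding-free brain region may not exist: Section 2.1 says diffuse inflammation affects all regions, and Section 2.2 finds COX-1 in all brain areas. Section 2.1 also offers a selection principle and admits that the ratio is silent on a global increase. The Section 9.1 hypothesis already concerns lesions, and the study is a pilot.

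All of this stands as a limit on size. None of it fixes the denominator or makes the mirror ratio a test of the Section 9.1 definition.

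Three stronger readings are tempting and not supported:

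- *The denominator would decide most results.* The 54-98% disagreement needs both a lesion with normal COX-2 and a binding-free comparator. The protocol expects the first not to hold and gives reason to doubt the second.
- *Selection on blocked scans inflates false positives.* In the case modelled it tilts errors towards falls but leaves two-sided error near 5%. With no stated rule, the actual effect cannot be computed.
- *The mirror is the wrong region, or a positive result is unsafe.* A true fall against the mirror means that the lesion's displaced fraction exceeds the mirror's, which is displaceable binding provided the mirror's is not negative. Lesion excess is a legitimate question, and the difficulty lies with a null.

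**Conclusion.** The point holds, and the plan is wrong as written where it ties this ratio to the stated objective. The denominator is open and is to be picked from the trial's own blocked scans. If it is the mirror, the test addresses lesion excess only, so a null cannot be read as undetectable COX. The Section 2.1 step from a null in lesions to an unlikely global increase fails.

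The cancellation is exact and needs no assumption about SD. The sizes do rest on assumptions: healthy-brain COX-2 figures used as a proxy for SUV, complete blockade, 11 completers and assumed SDs. Within them, the choice matters for the verdict when lesion COX-2 is near normal or about doubled, and hardly at all from threefold upwards. For COX-1, half of the primary endpoint, the documents give no displaceable brain fraction, so no magnitude can be stated. The change should be made before any blocked scan from an MS participant is analysed.

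**What to change.** 1. Replace the selection sentence in Section 2.1. In Section 9.4.2 name one primary reference region per tracer before any MS blocked scan is analysed. The mirror region the protocol already favours will serve, drawn on the 7T MRI blind to PET, with lesion voxels masked out using the existing segmentation.
2. Keep other regions, and the check of the reference on the blocked scan, as sensitivity analyses.
3. State in Sections 9.1 and 9.4.2 that the ratio tests lesion binding in excess of the contralateral region and that a null is not evidence of undetectable COX.
4. Align the objective wording in Sections 1.1, 2.3.3, 3 and 4.2; otherwise the mismatch remains. Delete or correct the inference about a global increase in Section 2.1.
5. Report baseline-to-blocked changes in lesion SUV and reference SUV separately, with confidence intervals. These are supporting evidence only: without an arterial input, a change in raw SUV cannot be separated from a change in the tracer reaching the brain.

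The cost is wording and a mask subtraction on images already planned, with no new scans or participants. The downsides are a narrower primary claim and a locked region that may not prove the best in hindsight.
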